**Table 1: Justification for the Scientific Premise of the HEALTH Study**

***Scientific Premise: HIIT will lead to better physical function and reduced patient-reported fatigue, compared with CME in older PWH.***

| Existing Support for the Premise   | How This Study Extends the Evidence  |
|--|--|
| Exercise is associated with improved physical function & reduced symptoms in PWH.                       | Well-powered, prospective, rigorous, experimental data will definitively answer this question and provide evidence of differential response by sex or other characteristics. |
| HIIT leads to greater physiological improvements vs CME in HIV-uninfected populations with chronic disease. | HIV-specific data accounting for HIV-associated impairments in physical function, fatigue, & mitochondrial activity.   |

**Overall significance of knowledge to be gained (Table 1):** As detailed above, even with effective ART, aging PWH experience impairments in physical

**HIIT improves adherence to regular physical activity/exercise.**

Behavioral support for self-directed exercise following supervised exercise will address maintenance of exercise in PWH.

function and disabling fatigue at higher rates than their peers without HIV. These impairments can further limit activity and contribute to a vicious downward spiral. One of the only interventions we can offer to preserve physical function and decrease fatigue is regular exercise, however older PWH face barriers to initiating and maintaining exercise, and may not have the same bioenergetic response to the exercise stimulus, limiting the physiologic response. HIIT is an innovative approach to exercise that may overcome some of these barriers, and has been shown safe, effective, and desirable to older adults with comorbidities. This investigation into the potential superior benefits of HIIT will provide patients and providers with evidence on the most effective exercise and behavioral interventions to extend *healthspan*, in the face of many comorbid conditions often experienced by older PWH.

Our application includes several innovative features responsive to the National Institute of Aging's goal of improving the health, well-being and independence of adults as they age. **First**, our findings will advance the interdependent science of aging by describing the clinical, biochemical, and physiological effects of HIIT compared to CME on physical function and fatigue. Such data in any older population are almost non-existent. We will contribute to existing knowledge by testing these exercise regimens in a chronically-ill, heavily-fatigued population (PWH). **Second**, despite the well-recognized effects of HIIT and CME on mitochondria, little is known about the effect of these interventions on mitochondria in PWH (with existing impairments in function) and far less in women living with HIV. *This is particularly novel because, age, HIV, and even modern ART appear to have deleterious effects on mitochondrial activity*. The HEALTH study is designed to address this gap and generate new knowledge on the local (skeletal muscle) and systemic (PBMCs) mitochondrial effects. We will enroll sufficient number of women ( $n=25$ ) to describe sex effects. **Third**, with 25% women, we will be uniquely poised to examine sex-specific responses to exercise intensity, including changes in physical function, fatigue, bioenergetics, and exercise adherence. **Fourth**, previous studies examining how to sustain exercise in PWH have either been cross-sectional or used single methods. Our integration of longitudinal quantitative (i.e., accelerometry) and qualitative (i.e., interview) methods, coupled with our detailed mixed methods analysis (see below), will better illuminate how to sustain the habit of exercise in this population. **Fifth**, previous exercise interventions in PWH are single-site, limiting generalizability. By harnessing the experience and infrastructure of two diverse sites, we will create high-quality, reproducible data that can be generalized to the larger population of older PWH living in the U.S. **Sixth**, this study uniquely incorporates an exercise adherence component to help support long-term sustainability and maintenance of the exercise habit. By systematically studying the long-term adherence of HIIT and CME, we will advance behavioral science in this area thus allowing us to develop and disseminate strategies to improve the long-term health status of older adults in diverse populations.

## II. Preliminary Studies/Progress Report:

Exercise Improves Physical Function. In our exercise intervention of 69 older adults (32 PWH), we observed significant improvements in physical function on nearly all physical function measures, regardless of serostatus (Figure 2a). Compared to HIV-uninfected participants, PWH had significantly greater percent improvements in  $VO_{2peak}$  (endurance) between weeks 0-12, and greater percent improvement in 400-MWT and stair climb between weeks 13-24. When we compared changes in physical function by exercise intensity (Figure 2b), as indicated with the pink bars, PWH randomized to higher intensity continuous aerobic + resistance experienced *greater* gains in strength, with a trend towards greater improvement in 400-MWT.

[figure not shown]
PWH recognized additional exercise benefits beyond objective assessments, described in focus groups: "The thing about exercise is as soon as you start doing it, you start feeling good" and "In a very short period of time you can go from being a couch potato, from being a blob, to feeling good...your mood changes and you start to feel like, my god, I'm happier." Decreased fatigue was readily apparent: "Well, running up and down the stairs after dogs and being on my feet for 5 hours straight. That's fantastic. I mean, normally it was like find me a chair. *Now I have more energy*".

Greater quantity or intensity of PA is associated with less fatigue in PWH. In a study of 109 PWH (mean age 53 years), we found that, after controlling for age and gender, greater cardiorespiratory fitness (of which exercise is a primary driver) was associated with lower levels of fatigue ( $\beta = -0.163$ ;  $p < 0.01$ ). To determine if the inverse associations between PA and fatigue held across populations we conducted the largest study of symptoms in PWH to date. In 5,370 PWH, fatigue was the most frequent (reported by 56%) and burdensome symptom. After adjusting for demographic and

HIV characteristics, higher intensity PA was associated with lower fatigue. Specifically, sedentary participants were almost twice as likely to experience more burdensome fatigue compared to those who engaged in moderate-intensity PA (OR 2.2 [95% CI 1.9, 2.6]), and almost five times as likely when compared to those who engaged in higher-intensity PA (OR 4.7 [95% CI 3.9, 5.6]). Lastly, in our exercise intervention, we found that baseline fatigue scores were 12.5 points worse in PWH compared to uninfected participants. Improvements in fatigue were significantly *greater* among participants randomized to high vs moderate-intensity exercise (3.9 [1.1, 6.6] vs -1.4 [-3.1, 0.2;  $p=0.002$ ).

**Mitochondrial dysfunction (induced by age, HIV, and even contemporary ART) may underlie physical function impairments and fatigue in PWH.** Skeletal muscle mitochondria of men with HIV on ART (including more mitochondrial toxic therapy such as zidovudine) had 17% lower ATP content and reduced oxidative enzyme activity (i.e., citrate synthase and  $\beta$ -HAD activity) compared to uninfected controls. Moreover, oxidative enzyme activity was directly related to aerobic capacity ( $VO_{2peak}$ ), suggesting that greater skeletal muscle mitochondrial impairment underlies poorer aerobic fitness among PWH, despite effective ART. **We obtained *vastus lateralis* skeletal muscle biopsies before and after our 24-week exercise intervention.** At baseline (Figure 3), slower 400-MWT was associated with mitochondrial components: lower citrate synthase activity (CS;  $p=0.07$ ); cytochrome complex 1 ( $p=0.03$ ), 3 ( $p=0.08$ ), and 4 ( $p=0.001$ ); manganese superoxide dismutase (MnS,  $p=0.03$ ) expression; and greater voltage dependent anion channel expression (VDAC; a mitochondrial protein regulating exchange of ions between the mitochondria and cytosol,  $p=0.03$ ).

Age-related loss of skeletal muscle quality and quantity are significant contributors to functional decline. Declines in both muscle quantity (mass) and quality (degree of fatty infiltration) begin in the 3rd or 4th decade of life. With aging, PWH experience greater than expected declines in lean mass (a proxy for skeletal muscle mass), which has been closely linked with poorer physical function. Furthermore, PWH appear to experience greater declines in muscle quality with increasing age, compared to HIV-uninfected controls (**Fig 2**). The *quality* of the muscle may provide a similar or better estimate of subsequent complications than muscle quantity. Multiple large cohort studies of older adults without HIV have shown strong associations between lower quality (i.e., fattier or less dense) muscle and poor physical function, hospitalizations, falls, and fracture. Exercise is an effective intervention to improve both muscle quantity and quality among older adults. We have previously shown gains in muscle *quantity* in the setting of supervised exercise, although attenuated among PWH. Whether PWH experience similar improvements in muscle *quality* with exercise, and whether these changes are directly related to improvement in physical function, are unknown.

Exercise Does Not Completely Restore Mitochondrial Function. In our exercise participants, at baseline ( $n=40$ ; 18 PWH), PWH had lower CS activity and greater VDAC (Fig 3a). Compared to controls, the mitochondrial adaptations to exercise training ( $n= 31$ ; 15 PWH) at moderate or high intensity were blunted in PWH as evidenced by significantly smaller increases in CS activity and protein expression of MnS, PGC-1 $\alpha$ , and cytochrome complex (C4) (Fig 3b). Sample size precluded further analysis of an exercise intensity effect on mitochondrial respiration rate and electron transport activity. *However, these preliminary findings suggest that a stronger exercise stimulus (e.g., HIIT) may be necessary to stimulate mitochondrial adaptations in older PWH compared to older uninfected adults.*

[figure not shown]
[figure not shown]
In combination, these data suggest differences in the skeletal muscle and metabolic adaptations among PWH, both at baseline and in response to exercise training. *Whether these responses are due to impairment in the muscle itself, impairment in skeletal muscle oxygen extraction and utilization, or impaired muscle substrate delivery is difficult to discern, but could have a major clinical impact on targeted interventions to preserve muscle function among PWH.*

In addition to physical function limitations, impairments in aerobic capacity have been reported among asymptomatic PWH as young as late adolescence and into older age.

Peak oxygen consumption (peak  $\text{VO}_2$ ) obtained by graded exercise testing characterizes the whole body response to exercise. Multiple factors may impact aerobic capacity including impaired oxygen delivery to tissue, impaired oxygen uptake at the tissue level, or an uncoupling of blood flow versus metabolism. In the general population, limitations in aerobic capacity are consistently associated with premature mortality. Prior studies of PWH in the early years of ART suggest that even well-suppressed PWH may have impaired peripheral tissue oxygen extraction or utilization despite obtaining peak  $\text{VO}_2$ . However, participants in these studies were relatively young (age 30s-40s) with a shorter duration of ART (mean 40-45 months). Increasing age and duration of ART and HIV may have different effects among people aging with HIV in the current treatment era.

Insufficient substrate delivery to muscle tissue may also contribute to impaired exercise capacity in PWH, as a result of decreased cardiac output, peripheral artery disease, or microvascular impairment at the level of the tissue. Indeed,

increasing age and ongoing inflammation contribute to a markedly higher risk of cardiovascular disease among PWH; peripheral artery disease also occurs more frequently among PWH than uninfected controls. Increasing evidence also implicates microvascular dysfunction in the pathogenesis of both coronary and peripheral vascular disease risk in PWH, as a consequence of chronic inflammation and immune activation. Among older adults with HIV, cardiovascular disease is strongly associated with impaired physical function and frailty. Although less is known about the functional implications of peripheral artery disease and microvascular disease among older PWH, the implications in other populations are apparent: among older asymptomatic adults without HIV, lower ankle-brachial indices (indicating impaired blood flow) were strongly associated with slower 400-m walk time (MWT). Members of our team have consistently found that microvascular disease is a major determinant of impaired exercise tolerance in other populations without HIV.

**Figure 4.** Conventional methods measure single, isolated parameters, rendering them incapable of assessing the interdependent physiologic processes. vPIVOT's simultaneous, interleaved approach provides a comprehensive hemodynamic and metabolic tool to measure the individual, as well as coordinated processes.

Existing methods to probe the underlying mechanisms of exercise intolerance are only capable of evaluating a single component of the vascular or metabolic response (Fig 4). For example, vascular function has been assessed by measuring blood flow changes evoked by a vasoactive stimulus (e.g. exercise, induced ischemia) in the large artery or at the tissue-level. However, by measuring macro-vascular and microvascular systems in isolation, it is impossible to resolve the contribution of resistance arteries versus capillaries on the measured vascular reactivity. Additionally, these flow responses on their own do not account for differences in underlying metabolic mediators. Measures of mitochondrial physiology (e.g., Oroboros) test function in an ideal state with adequate substrate. P-magnetic resonance spectroscopy (MRS) can provide an *in vivo* measure of metabolism in skeletal muscle but, P-MRS is non-localized and the measurement of oxidative capacity cannot differentiate between reduced substrate delivery versus mitochondrial dysfunction. **To develop a comprehensive mechanistic understanding of muscle's response to exercise among PWH, the simultaneous contributions of blood flow, oxygen extraction, and oxidative metabolism must all be resolved.**

The health benefits of an exercise intervention would be more meaningful if exercise was maintained thereafter. Despite high exercise adherence (92%) during our intervention, most of our participants returned to their pre-intervention sedentary habits. Indeed, <50% reported exercising ≥1 day/week at 12 weeks post-intervention. The marked gains in physical function and exercise self-efficacy (>70% felt “a lot more confident in my ability to exercise”) did not carry over to self-directed exercise. These findings clearly point to a need for *innovative interventions incorporating behavior change strategies*. Regular PA over the lifespan is critical to the health of our nation, particularly among those with multiple chronic health conditions, such as adults aging with HIV. A number of qualitative studies, including our own, have explored attitudes towards PA among diverse PWH and have identified several influencing factors, such as comorbidities, self-efficacy, social support, and accessibility of safe environments for exercise. In focus groups of older PWH in Colorado, participants shared barriers to routine PA, including a lack of social support, loneliness, low exercise self-efficacy (i.e., not sure what to do), and a negative perception of the gym culture. Every group had unprompted discussion about social isolation, or loss of friends or partners due to HIV or other causes, threatening the important social support motivator for exercise. **Many common and unique barriers limit uptake of exercise behaviors among older PWH; empowering this population with tools to overcome these barriers is essential to creating sustainable PA interventions.**

In summary, our preliminary data suggest a strong relationship between PA, physical function, and fatigue with greater benefits seen with higher intensity activity. Based on data from our prior exercise intervention, we anticipate that higher intensity exercise (e.g., HIIT) is likely to lead to greater improvements in physical function and reductions in patient-reported fatigue (**Aim 1**) compared to CME. We further hypothesize greater changes in mitochondrial bioenergetics with HIIT, and that these changes will be related to improved physical function and fatigue (**Aim 2**). We expect that HIIT will result in greater exercise satisfaction and likelihood of long-term continuation of exercise (**Aim 3**). Using a coaching intervention for self-directed exercise that combines motivational interviewing and personalized support during the maintenance phase (Aim 3), we seek to develop the ideal “cocktail” to promote healthspan among older PWH in the current era of ART.

## IV. Research Methods

### A. Outcome Measure(s):

#### Primary Outcome Measures

1. Change in 400-meter walk test (MWT) from week 0-16.

#### Secondary Outcome Measures

1. Change in Lee Fatigue Scale (LFS) from week 0-16.
2. Change in 400-MWT from week 0-28.
3. Change in LFS from week 0-28.
4. Change in state 3 respiration (from skeletal muscle) from week 0-16.
5. Change in state 3 respiration (from PBMCs) from week 0-16.
6. Total Actigraphy-measured time spent in physical activity per week and daily step count from week 17-28.
7. Perception of physical activity (qualitative interviews) at weeks 0, 16, 28.

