#### Exploratory Outcome Measures

1. Change in 1-RM adjusted for lean body mass from week 0-16.
2. Change in VO2 maximum from week 0-16.
3. Change in Short Performance Physical Battery (SPPB) and modified SPPB from week 0-16 and 0-28

4. Change in PROMIS-measured fatigue from week 0-16 and 0-28.
5. Change in DXA-measured total body fat and lean body mass from week 0-16.
6. Change in electron transport chain activity (skeletal muscle) from week 0-16.
7. Change in electron transport chain activity (PBMCs) from week 0-16.
8. Change in mitochondrial content (skeletal muscle) from week 0-16.
9. Change in mitochondrial content (PBMC) from week 0-16.
10. Change in physical function outcomes, patient-fatigue and physical activity adherence from week 17-28 by exercise and coaching intervention.
11. Change in mitochondrial bioenergetics, physical function and fatigue at baseline, week 16, and change from 0-16
12. Change in self-reported 3 day diet intake from week 0-16.
13. Change in stool microbiome and short-chain fatty acids from week 0-16
14. Change in muscle fat by proton density fat fraction (PDFF), intramyocellular lipid (IMCL) and extramyocellular lipid (EMCL) from week 0-16
15. Change in oxidative phosphorylation (OxPhos) from week 0-16.
16. Change in mean VO2 response *in the gastrocnemius and soleus muscles* from week 0-16.
17. Change in lean muscle quality and quantity from week 0-16 by muscle ultrasound.
18. Explore the barriers and facilitators for non-participation in an exercise-related clinical trial.
19. Change in cognitive functioning (i.e., global and domain T scores) and subjective cognitive symptoms (self-report questionnaires) from 0 to 48 weeks.
20. Change in blood markers (neurotrophins [e.g., BDNF], growth factors [e.g., VEGF], pro-inflammatory cytokines [e.g., IL-6]) from 0 to 48 weeks
21. Change in neuroimaging markers: cerebral blood flow, resting state functional connectivity, and brain volume), from 0 to 16 weeks (UAB SITE ONLY)
22. Psychological mechanisms of adherence to exercise at 48 weeks (measured with questionnaires and text message surveys)

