#### **Procedures/Outcome Measures:**

**Randomization.** After the conclusion of the exercise intervention, participants will be randomized 1:1 (with even allocation of HIIT vs CME) to receive the coaching or control intervention (details below).

**Quantitative Measures.** PA will be measured with a widely-used and validated measure, the ActiGraph accelerometer (ActiGraph, LLC, Fort Walton Beach, FL), as described in Aim 1. **Primary exercise endpoints** are (1) time spent in moderate-to-vigorous PA (MVPA), and (2) steps per day.

These endpoints will be set with the adult cut-points for tri-axial accelerometers. All participants will complete a daily log during the maintenance phase to track aerobic and resistance exercise. This log will include the time, type, duration, and setting of exercise completed each day. It will be triangulated with the accelerometry data and reported descriptively.

**Qualitative Measures.** **One-on-one Interviews (this will be optional).** First, we will pilot test an interview guide on 2-3 PWH at UW and UCD-AMC and revise it accordingly. A final guide will be used to direct subsequent interviews consistently at both sites. The interviews will take place in a secure, private location. Questions will address the participants' perceptions of exercise; experiences with HIIT, CME, or resistance training; the coaching intervention; and what they think will help them sustain PA over the long-term (Fig. 4). If a participant withdraws from the study, he/she may be offered a withdrawal interview to explore reasons for withdrawal and/or ways to improve the study intervention. Interviews will take ~ 30 minutes, be audio-recorded, and transcribed verbatim. [name] has over 15 years of experience designing, implementing, and analyzing data from qualitative studies and has successfully trained and managed qualitative data collectors across sites, obtaining high-quality data.

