## F. Data Analysis Plan:

**Statistical Considerations.** We hypothesize that among older PWH, HIIT will lead to better physical function and reduced fatigue through improvements in mitochondrial bioenergetics compared with CME.

**Sample Size Calculations:** We assume a 1:1 randomization to HIIT or CME balanced by site, sex ( $\geq 25\%$  women) and age category (50-59, 60-69, and 70+) with a conservative 20% dropout rate, resulting in 40 evaluable participants/group. The second randomization at week 16 and will also be balanced by initial randomization (2x2 factorial design). Aim 1 and 2 power calculations assume two-sided, 2-sample/paired *t*-tests for between/within group comparisons of the change from baseline with a 0.05 significance level. We assume conservative within subject correlations ( $\rho$ ) of 0.7 or 0.5 to estimate the standard deviation (SD) of the outcome change, larger correlations and repeated measures will result in additional power. The Aim 1 primary outcome is change in 400-MWT. We assume an effect size comparable to Toohey, an intervention comparing HIIT to CME among middle-aged (mean age 51, SD 12 years) cancer survivors that resulted in a mean (SD) difference of 97 (82) and 36 (68) meters in 6-minute walk distance among HIIT and CME, respectively. Using  $\rho=0.7$ , and a sample size of 40/group, we will have  $>88\%$  power to detect a comparable *between* group differences of 45 (38) and 20 (38) second improvement in 400-MWT in HIIT and CME, respectively. For reference, in our prior exercise study, PWH had a 25 second improvement in 400-MWT. This also provides  $>99\%$  and  $>81\%$  power to detect *within* group differences in the HIIT and CME arms. For morning and evening fatigue, we assume a baseline mean of 19(8) and 27(8) points, respectively ([name], unpublished data). With  $\rho=0.5$ , and a sample size of 40/group, we will have  $>80\%$  to detect a change of  $\geq 27\%$  and  $\geq 20\%$ , respectively. The primary Aim 2 outcome is change in State 3 respiration. Based on Robinson, we estimate a baseline mean (SD) of 580 (180) pmol  $O_2$ /min/mL using  $\rho=0.5$ . This provides  $>81\%$  power to detect a difference in the change of 50% (HIIT) and 30% (CME). The muscle substudy is considered exploratory, however, we anticipate adequate power. Using preliminary data, combining HEALTH+ exercise groups (N=24), provides  $>80\%$  power to detect a change of -8.7% in MRI-PDFF of HEALTH+ participants. For within exercise group (CME or HIIT) comparisons, a sample size of 12 provides  $>80\%$  power to detect a difference of -12.5%. For the CME versus HIIT change from baseline comparison, a sample size of 12 per group provides  $>80\%$  power to detect group differences of 9.8%. For the change in OxPhos, combining HEALTH+ exercise groups (N=24, 3 dropouts/group), provides  $>80\%$  power to detect an OxPhos change of 0.039. For within exercise group (CME or HIIT) comparisons, a sample size of 12 provides  $>80\%$  power to detect an OxPhos difference of 0.055. For the CME versus HIIT change from baseline comparison, a sample size of 12 per group provides  $>80\%$  power to detect group OxPhos differences of 0.056. For the change in aim 3, combining HEALTH+ exercise groups, a sample size of N=24 (3 dropouts/ group), provides  $>80\%$  power to detect a 21%  $\dot{V}O_2$  change in HEALTH+ participants. For within exercise group (CME or HIIT) comparisons, a sample size of 12 provides  $>80\%$  power to detect 33% change in  $\dot{V}O_2$ . For the CME versus HIIT change from baseline comparison, a sample size of 12 per group provides  $>80\%$  power to detect a 30% difference in the 16-week change from baseline.

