## Analysis Approaches

### Analysis Plan:

**Aims 1 and 2:** Baseline (week 0) characteristics will be compared between groups prior to comparisons of endpoints, with log transformation for normality, as appropriate. Age, sex, baseline CD4 count and/or VACS score, smoking, exercise intensity and body mass index (BMI) will be considered for inclusion into regression models; although if matching and/or balance by age and sex is achieved, these will be precision variables, rather than confounders. Differences in response by antiretroviral therapy (ART) class; prior ART exposure to zidovudine, stavudine, didanosine; use of statin; psychiatric medication burden; and use of hormone replacement therapy will also be explored. Given repeated measurements, a linear mixed effects model will be used with change from week 0 as the primary outcome.

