**Aim 3:** Quantitative data will be summarized and used to describe physical activity (PA) amount and mode and then categorize the sample (see below for synthesis of data). After redacting identifying information, verbatim transcriptions of interviews will be entered into Dedoose, a secure, cloud-based qualitative analysis program. Our quality assurance protocol will include checking 25% of the transcripts to verify accuracy of the transcriptions and double-coding 10% of the transcripts to ensure inter-coder reliability of 80% or greater. Under MPI [name]'s direction, all responses will be analyzed using standard qualitative analytic techniques: identification of themes; coding of participants' responses by these themes performed independently by two team members (who have graduate-level training in qualitative coding); resolution of any coding discrepancies will be done by a third team member. To ensure consistency, a codebook will be developed to create universal definitions for each code. The codebook will contain all codes, their definition, and exemplar quotes and will be iteratively tested until all coders agree it captures the breadth and depth of the perceptions about HIIT, CME, the coaching intervention, and sustaining long-term PA in PWH. We will search for *a priori* codes that describe the perceptions of HIIT and CME and long-term PA maintenance based initially on our literature review. Significant inductive (emerging) codes will also be identified. Coded items will be grouped together into distinct themes. Group analysis meetings will be held to compare independently-developed codes for similarity and further direction. This data reduction method, encompassing a team-based analysis, creates a robust iterative process through which the data are thoroughly discussed and analytical consensus achieved.

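### No written model for the week 0-28 walk and fatigue outcomes includes the coaching factor randomised at week 16; adding it would define the week-28 contrast and slightly sharpen it

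*Combined protocol and SAP*

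**What the plan says.** Section IV.A, Secondary Outcome Measures, lists "Change in 400-MWT from week 0-28" and "Change in LFS from week 0-28". It states no contrast and no model for either.

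The second randomisation is described under Aim 3, Procedures/Outcome Measures: "participants will be randomized 1:1 (with even allocation of HIIT vs CME) to receive the coaching or control intervention". Sample Size Calculations (Section F) says that this randomisation "will also be balanced by initial randomization (2x2 factorial design".

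The analysis text is in four places:

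- **Analysis Plan, Aims 1 and 2.** On candidate covariates: "Age, sex, baseline CD4 count and/or VACS score, smoking, exercise intensity and body mass index (BMI) will be considered for inclusion into regression models". On the model: "a linear mixed effects model will be used with change from week 0 as the primary outcome". Coaching is not mentioned, and no fixed-effects formula or week-28 contrast is given.
- **Analysis Plan, Aim 3.** "Quantitative data will be summarized and used to describe physical activity (PA) amount and mode and then categorize the sample". The rest is qualitative coding and a mixed-methods synthesis, with no inferential factorial model.
- **Exploratory Outcome Measures, item 10.** "Change in physical function outcomes, patient-fatigue and physical activity adherence from week 17-28 by exercise and coaching intervention". Both factors are named, but at exploratory level, over a different interval and with no model.
- **Cognitive Substudy Statistical Analysis, stage 2.** A mixed model with exercise, coaching, their interaction and the time interactions is written out for months 4 to 7, for cognitive scores only. Interaction terms that are not significant are to be removed.

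**The concern.** By week 28 half the participants in each exercise arm should have had 12 weeks of coaching intended to sustain exercise. Any effect of coaching on walk time or fatigue is then part of the week-28 variation. If the model has no coaching term, that part goes into the residual, and the standard error of the HIIT-CME contrast is larger than the design requires.

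The contrast itself is also undefined. Once a second factor is in play, the HIIT-CME effect at week 28 can mean the average over coaching levels, or the effect within coached or uncoached participants. The Background section expects exercise and coaching to act together, so these could differ. The parent trial's week-28 secondary outcomes are less fully specified than the substudy's cognitive scores.

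**Working it through.** **Inputs.** From Sample Size Calculations: improvements of 45 s and 20 s in 400-MWT (difference 25 s), SD 38 s, 40 evaluable per group, two-sided 0.05. These are week-16 planning values; none are given for week 28, so using them there is an assumption. The documents give no coaching effect on walk time or fatigue. I call it c and show a range.

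**The plan's own figure.** The stated power for the week-16 contrast is above 88%. With these inputs, SE = 38 × √(2/40) = 8.50 s, 25/8.50 = 2.94, and power = Φ(2.94 − 1.96) = 83.7% (82.8% with the t distribution). The stated figure does not reproduce. That is a separate matter; I use 83.7% as the reference.

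**Cost of omitting coaching.** A balanced two-level factor with effect c adds c²/4 to the variance, so the SD without the factor is √(38² + c²/4).

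| Assumed c | SD without coaching term | SE inflation | Power without term (normal) |
|---|---|---|---|
| 5 s | 38.08 | 0.2% | 83.5% |
| 10 s | √(1444 + 25) = 38.33 | 0.9% | 83.1% |
| 15 s | 38.73 | 1.9% | 82.3% |
| 20 s | 39.29 | 3.4% | 81.2% |
| 25 s | √(1444 + 156.25) = 40.00 | 5.3% | 79.8% |

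If 38 s is read as the total SD instead, the inflation at 25 s is 1/√(1 − 0.108) − 1 = 5.9%.

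**Simulation check** (20,000 replicates, 20 per cell). The mean HIIT-CME estimate is 25.0 s with or without the term. Power without and with the term is 82.4 and 82.8% at c = 10 s, and 80.3 and 83.3% at c = 25 s. Because allocation is balanced, the true sampling error stays at 8.50 s and only the estimated SE is inflated. By the normal approximation, a nominal 5% test then has an actual size of about 4.8% at 10 s and 3.9% at 25 s.

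**Larger sample.** 180 randomised with 20% dropout leaves 180 × 0.8/2 = 72 per arm. Power is then 97.7% with the term and 96.3% without it at c = 25 s.

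**Fatigue.** The inflation depends only on c/SD. The range above is 10/38 = 0.26 to 25/38 = 0.66 SD. The planning values for LFS (SD 8, correlation 0.5) give a change SD of 8 × √(2 × 0.5) = 8 points, so the same inflation corresponds to coaching effects of about 2.1 to 5.3 points.

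**Dropout.** With no interaction, the shift in the HIIT-CME contrast from omitting coaching is c × (coached share of HIIT completers − coached share of CME completers). If coached and control participants drop out at different rates, but equally so in both exercise arms, the two shares stay equal and the shift is zero.

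**Interaction precision.** At 20 per cell the interaction has SE = 38 × √(4/20) = 17.0 s, twice that of the averaged contrast. Selecting it by significance would therefore be unreliable.

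**The case against.** The strongest reply is that the plan is silent and has not chosen to omit coaching. The Aims 1 and 2 paragraph writes out no arm, visit or site term either, and both aims are 16-week comparisons, made before coaching starts. The design is declared factorial, and exploratory item 10 analyses function and fatigue by both factors. A reader might infer that the sponsor has decided to leave coaching out at week 28; no text says so. The HIIT-CME contrast at week 28 is likewise inferred from Aim 1.

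All of that stands, but it does not supply a model. Item 10 is exploratory, covers weeks 17-28 and has no formula. The Aim 3 analysis is descriptive.

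The second reply is that the loss is trivial. The coaching effect is assumed, and the top of the range equals the whole assumed HIIT-CME difference. This also stands: the precision argument alone is weak.

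A reader might also infer that differential dropout between coached and control groups would unbalance the exercise comparison. It does not do so by itself: dropout would have to depend on the exercise-by-coaching combination. The Missing Data section plans several dropout sensitivity analyses, though none mentions coaching.

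**Conclusion.** The point holds as an omission with a small consequence. No written model for the two week 0-28 secondary outcomes includes the factor randomised at week 16, and the week-28 HIIT-CME effect is not defined with respect to it.

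If coaching is omitted, the contrast remains unbiased for the effect averaged over coaching and the test is slightly conservative. The SE is about 0.9 to 5.3% too large for an assumed coaching effect of 10 to 25 s. That is from under 1 to about 4 power points at 40 per arm, and less at 72. These figures rest on a residual SD of 38 s carried over from week 16, on balanced allocation, and on a coaching effect that the documents do not give. They do not support a claim of bias or of a serious loss of power. The change is still worth making: it is free, uses a group the trial already randomises, defines the contrast and yields an inferential coaching estimate.

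**What to change.** In the week 0-28 mixed models for 400-MWT and LFS, add coaching and exercise-by-coaching terms for visits after week 16, set to zero at week 16 and before. With that coding, participants who leave before the second randomisation stay in the model. Specify the terms so that the week-28 effects can be read off.

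Define the week-28 HIIT-CME effect as the equally weighted average over the two coaching levels. Without this, ordinary 0/1 coding would make the exercise coefficient the effect among uncoached participants only, with SE 38 × √(2/20) = 12.0 s in place of 8.5 s. Report the coaching main effect and the interaction beside it, with confidence intervals.

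Keep the interaction whatever its p-value. The cognitive substudy's stage 2 model is a useful starting point, but its rule for removing non-significant interaction terms should not be copied.

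The cost is a few sentences in the analysis plan. No new data, visits or participants are needed.
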